- 2) The rate of responders (defined as improvement of LVEF  $\geq$  10% points) with HF medical therapy alone during observation period will be less than 15% *in subjects with CM associated with frequent PVCs*. In contrast to HF medical therapy alone, RFA and AADs will have a responder rate of *at least 35% in the same population*. *Furthermore, RFA will have a greater 1-year response rate when compared to AAD therapy.*
- 3) *RFA will have a lower rate of composite adverse events (worsening NYHA class, HF admission, treatment side effects & complications, and death), arrhythmia burden and a better long-term tolerance than AADs.*
- 4) The prevalence of CM (LVEF  $\leq$  45%) and frequent PVCs ( $\geq$ 10% burden) is largely under recognized in subjects undergoing ambulatory ECG Holters (Part II).

**Methods.** To test our hypotheses, we propose: 1) a clinical pilot study to prove the feasibility of a large-scale multicenter clinical trial (PAPS study) of subjects with probable PVC-CM, and 2) screen near 20,000 consecutive ambulatory ECG Holter monitors of all participating centers to identify all subjects with probable diagnosis of PVC-CM (PVC burden  $\geq$ 10% and LVEF  $\leq$ 45%). The clinical pilot study will enroll between 36-39 subjects with frequent PVCs (burden  $\geq$ 10%) and CM (LVEF  $\leq$ 45%) and randomize them to either: 1) RFA or 2) AADs. Prior to treatment, a baseline cardiac MR will be performed if clinically indicated and be allowed a 3-month observation period. To assess the effects of PVC suppression, we plan to compare changes in LV function, rate of responders (defined above), PVC burden/arrhythmias and clinical/functional status (QOL, HF symptoms and admissions, NYHA class) and adverse events between observation period both PVC suppression strategies (RFA or AAD).

To identify the best PVC suppression strategy, we will perform similar comparisons between RFA and AAD treatment groups during a 12-month follow up using a Prospective Randomized Open, Blinded End-point (PROBE) study design. The treatment regimens will be compared in an intention-to-treat analysis.

Our study is *unique due to its multidisciplinary approach and design* including: 1) observation/control period that allows us to assess for spontaneous improvement of PVCs and/or CM, and 2) active treatment to all subjects, which will allow for easier subject enrollment and retention with minimal drop out.

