iii. *Observation – Visit 3.* Similar to Visit 1, appropriate data collection forms should be used to collect current medical therapy, NYHA functional class and Minnesota HF quality of life questionnaire (QOL). 12-lead ECG should be obtained if clinically indicated. Transthoracic echocardiogram should be performed to assess LVEF and a copy mailed to the Echo Core laboratory led by [name] III, M.D. The local PI and designated site staff will be able to log in to iRhythm's ZioReports to obtain the Zio Patch report that should include a 2-week PVC burden.

[figure not shown]
If PVC burden remains  $\geq 10\%$  and LVEF  $\leq 45\%$ , then the subject will either initiate antiarrhythmic drugs or undergo RFA procedure (see Section C: Description of the intervention/treatment) and will continue on protocol as scheduled. However, if these criteria are no longer met, the subject is considered a screen failure and is withdrawn from the study. In such a case, the treatment decision is solely at the discretion of the electrophysiologist caring for subject. Nevertheless, this subject will be included in a PVC-CM registry if consent was provided (described above Section A.1).

i) *Treatment – Visit 1.* This is considered the baseline visit where PVC suppression strategy assignment is initiated (either RFA or AADs). If the subject is randomized to RFA, we will request that sites complete the RFA data collection form which includes information during the RFA procedure as well as recovery, complications and hospital stay. EPS will be performed on their baseline medications, except for antiarrhythmic drugs class II (beta blockers) which will be held at least 5 half-lives prior to procedure. Beta blockers should be resumed after RFA.

iv. However, subjects randomized to AADs can have this visit combined with Observation-Visit 3. In addition, subjects in the antiarrhythmic (AAD group) will require a baseline TSH and LFTs (AST only) if amiodarone is chosen.

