c. 3. Transthoracic Echocardiogram. Scheduled 2D-Echocardiograms should be requested as noted on Table 2 if clinically indicated. Echocardiograms will be performed using a commercial system with a 5MHz standard cardiac probe with at least 70-80 frames per second. Echocardiography will be considered adequate if echocardiographic windows allow assessment of the following parameters, otherwise, echo contrast should be performed. LV function will be assessed by quantifying the calculated LVEF (Simpson's formula), fractional shortening (FS), LV end-systolic and diastolic dimensions (LVESD, LVEDD), LV thickness, left atrial (LA) size, mitral valve (MV) function, LV compliance (E/A ratio and E/E' ratio), and dyssynchrony. Interventricular dyssynchrony will be evaluated by RV and LV electromechanical delay (time from onset of QRS to the onset of pulmonary and aortic systolic flow, respectively). LV mechanics / dyssynchrony will be assessed by 1) septal to posterior wall delay, 2) PW-TDI maximum systolic motion delay between septal, anterior, posterior and lateral wall, and 3) 2D

speckle tracking strain analysis (radial, circumferential and longitudinal strain). A copy of the echocardiogram images should be sent to the Echo core laboratory (led by [name], III) for final interpretation by a cardiologist blinded to the randomization arm. Assessment of LVEF by echocardiography will be repeated during observation and treatment phases in order to assess changes in LV function during observation period and between PVC suppression strategies.

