c. 6. Complications, heart failure admissions and adverse events. *All events* including mortality, hospital admissions and heart failure exacerbations and treatment-related complications will be documented on each subject throughout the observation and treatment periods. Each center will report any adverse events to the Coordinating Center (McGuire VA Medical Center, Richmond VA) within 24-48 hours of the occurrence or knowledge of the event. *All SAE/hospital admissions, procedure complications and events will be evaluated and assigned by an event adjudication committee (see Section G. Ethical / Regulatory Affairs and documents: Human subjects and Data Safety Monitoring plan for details).*

*Participating centers will provide all available clinical data to respective core labs (echocardiogram, cardiac MR and Holter) and Coordinating Center (McGuire VA Medical Center) through REDCap with a case number without identifiers and treatment randomization as outlined in the Manual of Operations and Standard Operating Procedures manual.*

Of note, subject participation and results of this study will not change diagnostic testing (e.g. electrophysiologic studies for other indications) and medical management including medical therapy (unless safety drug interactions are clear) and indicated procedures (e.g. left heart catheterization). ICD implantation is not encouraged (but not prohibited) during the study as the CM may improve or even resolve after RFA of PVCs as recently shown by Penela et al..

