#### **E. Primary and secondary outcome measures.**

*The outcomes are divided in primary and secondary end-points (Table 3).*

*The primary end-points will consist of:*

1. *Improvement of LVEF after PVC suppression at 12-month follow-up.* This is chosen as primary-end point due to the known prognostic value of LVEF. The lower the LVEF, the higher the risk of sudden cardiac death and heart failure. This will compare the overall improvement or change in LVEF between RFA and AAD groups. This end-point will support that either RFA or AADs have an overall better outcome due to significant improvement of LV function with potential impact on morbidity and mortality associated with PVC-CM.

2. *Responders to PVC suppression strategy at 12-month follow-up* (See rationale under Section “Definitions” in 3rd paragraph of Aim 2). Assessment of the number of responders (delta LVEF  $\geq$  10%) after PVC suppression strategies (RFA or AADs) will assess the effectiveness of RFA and AADs to reverse or improve cardiomyopathy induced by frequent PVCs. Evidence that either RFA or AADs is superior to improve or even reverse LV dysfunction in subjects with high burden PVCs could have significant impact of morbidity and mortality including future heart failure and ventricular arrhythmias, and also may avoid ICD implantation.

*The secondary end-points will consist of:*

1. *Efficacy of RFA vs AADs groups to achieve successful PVC suppression at 12-month follow-up, defined as a reduction of PVC burden  $\geq$ 80% (regardless of LVEF change). Understanding the success rate of PVC suppression between RFA and AADs will help better determine the best treatment to those subjects with high PVC burden.*

2. *Composite end-point of adverse events at 12-month follow-up, including worsening in NYHA functional class (I-IV), number of HF and cardiac-related admissions, RFA complications and AAD adverse effects and cardiovascular death.*

This adverse event composite end-point is chosen to understand the overall complications and adverse effects/events related to RFA and AADs. Worsening of NYHA functional class will be defined as when/if the subject’s functional status worsens by one NYHA class. Hospital admissions will be defined as any visit to ED or hospital admissions related only to a cardiovascular event such as heart failure, angina, pre/syncope and palpitations.

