#### *Rate of responders to PVC suppression*

Besides improvement in LV systolic function, no study has been designed to demonstrate clinical benefits with either RFA or AADs. Clinical benefits are implied based solely on the improvement of LVEF. Based on prior retrospective and observational studies, the rate of responders (improvement of LVEF) to PVC RFA is estimated at 50-65%. Unfortunately, there is no recent data on antiarrhythmics due to the lack of recent studies. Our preliminary data from the CHF-STAT study demonstrates a response rate of 28% (Preliminary Data Section).

We plan to further identify the rate of responders after PVC suppression by obtaining the following primary end-points: 1) improvement in LVEF (determined by  $\Delta \text{LVEF} = \text{final LVEF} - \text{baseline LVEF}$ ) and 2) “responders” to PVC suppression (defined as change in LVEF  $\geq 10\%$ ). In addition, we will obtain QOL and NYHA functional class questionnaires (secondary end-point described above). Each subject will serve as its own control, since all data obtained will be compared between the end of 3-month observation period (control phase - prior to randomization) vs. 3-month after PVC suppression strategy, regardless of treatment randomization (RFA and AAD). We hypothesize that a PVC suppression strategy (RFA or AAD) is better than optimal HF medical therapy alone to improve LV function, HF symptoms, heart failure admissions, and avoid the need for defibrillator. *The PAPS pilot study will help us determine the rate of responders to PVC suppression strategy in order to properly estimate sample size and power the large randomized PAPS study.*

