#### Avoidance of bias

In order to avoid a high proportion of a single ethnic or racial group, we decided to involve multiple high-volume centers across the country. All participating centers will send all clinically indicated data (echocardiograms, CMR, ECG, and Holters) to the respective core laboratory, where the cardiologist will be blind to the assigned group, giving a final interpretation. All 2-week ambulatory ECG Holter monitors will be contracted to a single company (ZioPatch™, IRhythm Technologies, Inc.) and evaluated by the Holter core lab ([name]) to prevent differences in PVC detection algorithms. Finally, stratified randomization will ensure an equal distribution of subjects between PVC burden above and below 20%.

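### The plan masks the Echo core-lab reader to arm only, which does not protect the pooled before-versus-after LVEF comparison behind hypothesis 2

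*Combined protocol and SAP*

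**What the plan says.** **Masking of the reader.** Item c.3 of section C (Clinical Assessment and tests) sends echo images to the Echo core laboratory "for final interpretation by a cardiologist blinded to the randomization arm". Avoidance of bias repeats this for all core laboratories, "where the cardiologist will be blind to the assigned group, giving a final interpretation". Item c.6 says that sites supply core-lab data "with a case number without identifiers and treatment randomization as outlined in the Manual of Operations". That manual is not among the documents. Visit, date and reading order are not mentioned in any of these places.

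**Transfer of echoes.** Section B (Scheduled Visits) has copies sent visit by visit. The screening echo goes at Observation Visit 1. At Observation Visit 3, "Transthoracic echocardiogram should be performed to assess LVEF and a copy mailed to the Echo Core laboratory". Treatment Visits 3, 4 (if clinically indicated) and 6 follow the same pattern, and at Visit 5 sites send any echo done in between. No batching is described.

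**Use of LVEF.** There are two comparisons.
- Between arms: section E says of the first primary end-point, "This will compare the overall improvement or change in LVEF between RFA and AAD groups". Specific Aims attaches the PROBE design here: "similar comparisons between RFA and AAD treatment groups during a 12-month follow up using a Prospective Randomized Open, Blinded End-point (PROBE) study design".
- Before versus after, arms pooled: section F (Rate of responders) says "Each subject will serve as its own control, since all data obtained will be compared between the end of 3-month observation period" and "vs. 3-month after PVC suppression strategy, regardless of treatment randomization". Hypothesis 2 expects fewer than 15% responders on heart-failure therapy alone during observation and at least 35% with suppression.

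**The concern.** In a randomized comparison of arms, the reader must not know the arm. In the pooled own-control comparison the exposure is time: the echo was taken either before or after suppression. Hiding the arm says nothing about that. If a reader could tell that an echo was post-suppression and expected LVEF to rise, readings could shift upward. The shift would go straight into the within-subject change and the responder rate.

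This matters because section F names LVEF change and response as the primary end-points and, in the same paragraph, applies the own-control comparison to all data obtained. It also says that the pilot's responder rate will be used to size the full trial, so a biased rate would carry forward.

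**Working it through.** **1. The plan's own figure.** Inputs from Sample size justification: 12-month LVEF of 40% versus 35%, SD 10, baseline SD 5, within-subject correlation 0.25, type I error 0.05 (taken as two-sided), power 0.80, dropout 10%.
- n per arm = 2 × (1.960 + 0.842)² × 10² / 5² = 62.8, so 63.
- 63 / 0.90 = 70 per arm, 140 in total, as stated.
- SD of change = √(5² + 10² − 2 × 0.25 × 5 × 10) = 10.0, so an analysis of change gives the same n.

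**2. A drift d common to both arms, between-arm comparison.** The difference in mean change is (μ_RFA + d) − (μ_AAD + d) = μ_RFA − μ_AAD, so d drops out. A simulation (20,000 trials, 70 per arm, 10% random dropout, t-test on change, no site effect) agrees:

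| Drift at 12 months | Mean difference | Power |
|---|---|---|
| 0 | 5.01 | 0.796 |
| 3 | 5.02 | 0.796 |
| 5 | 5.02 | 0.798 |

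The cancellation is exact for the mean only. For responders, with the plan's mean changes of 15 and 10 and SD 10, the rates are Φ(0.5) = 69.1% and Φ(0) = 50.0%. With d = 3 they become Φ(0.8) = 78.8% and Φ(0.3) = 61.8%, so the difference moves from 19.1 to 17.0 points. If the arms do not truly differ, both rates move alike and no difference appears.

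**3. The same drift, pooled before-versus-after comparison.** Here d does not drop out. Assumptions: normally distributed change, responder threshold 10 points, true responder rate 15%, so (10 − μ)/SD = 1.036. The apparent rate is then 1 − Φ(1.036 − d/SD).

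The documents give no SD for the 3-month change, so a range is shown. SD 10 borrows the baseline-to-12-month value from step 1. SD 6.1 = √(25 + 25 − 2 × 0.25 × 5 × 5) applies if the SD is 5 at both times. SD 8 lies between.

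| SD of change | d = 1 | d = 2 | d = 3 | d = 5 | Drift that alone gives 35% |
|---|---|---|---|---|---|
| 6.1 | 19.1% | 23.9% | 29.2% | 41.3% | 4.0 |
| 8 | 18.1% | 21.6% | 25.4% | 34.0% | 5.2 |
| 10 | 17.5% | 20.1% | 23.1% | 29.6% | 6.5 |

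The last column is (1.036 − 0.385) × SD = 0.651 × SD.

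**The case against.** **Nothing says that the reader knows the visit.** This stands. One might infer from the visit-by-visit mailing that echoes are read in time order with their dates visible. Section B says when sites send copies, not when or how the laboratory reads them, and c.6 defers detail to a manual that cannot be checked here. What can be said is that the protocol does not state such masking. It does spell out wider masking elsewhere: the Event Adjudication Committee is also kept from TSH and LFT results because they could disclose allocation.

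**The plan does not claim PROBE protection for this comparison.** This also stands. A reader might think that the plan contradicts its own PROBE label. However, the Abstract and Specific Aims attach PROBE to RFA versus AAD, where the stated arm masking fits.

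**The randomized comparison is sound.** Agreed for mean LVEF change, as step 2 shows. The 140 is unaffected.

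**The size is conjecture.** Largely true. The drift has no source in the documents, LVEF is quantified by Simpson's formula, and the plan names no test for the paired comparison. A drift of 3 points falls short of 35% at every SD shown.

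**This is a pilot.** The Data Sharing Plan says that its data are not meant to settle the benefits of the suppression strategies. That lowers the stakes but does not remove them, because the responder rate is a stated output for sizing the next trial.

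**Conclusion.** The gap is real and limited. The protocol states masking to arm, and that serves RFA versus AAD. It states no masking to visit, date or order, and so gives no stated protection to the pooled own-control comparison. It does not follow that the reader is unmasked in practice, or that the between-arm result is at risk from a common drift.

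With an assumed SD of 10 and a true responder rate of 15%, drifts of 1, 2 and 3 points read as about 17.5%, 20% and 23%. With an SD of 6.1 they read as about 19%, 24% and 29%. Drift alone would have to reach about 4.0 to 6.5 points to produce the hypothesised 35%. These figures show sensitivity and are not an estimate of actual bias. The point merits a change because the safeguard is cheap, not because the pilot fails without it.

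**What to change.** In c.3 and in Avoidance of bias, state that for the analysis LVEF the Echo core laboratory reads each subject's echoes as one set, in random order, with visit label and date masked as well as arm. Include the sets of subjects withdrawn at Week 12, since they contribute to the observation-period responder rate.

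Two things should stay outside the masked read:
- Image-quality checks, which section G (Data collection) gives to the core laboratory, should continue on receipt.
- Any LVEF reading needed for the Week 12 eligibility check should stay on time and separate. The plan does not say whether the site or the core laboratory supplies it. If it is the core laboratory, that echo is read again, masked, for the analysis.

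If this is not adopted, label the before-versus-after LVEF result as not masked for time.

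**Cost.** No extra echoes are needed. The work is relabelling and batching, plus a second read of the Week 12 echo if the core laboratory decides eligibility. Core-lab LVEF arrives later. The interim analysis need not wait, because it uses the first 15 subjects to complete the 15-month protocol, whose sets will be complete. Masking will be partial, since PVCs may be visible on the recording. It does not remove regression to the mean or the effect of titrating medical therapy during observation (section B), so the comparison remains non-randomized.

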#### **D. Description of the intervention(s)/treatment(s).**

Prior to intervention, all subjects should complete a 3-month observation period consisting of a total of 3 visits. Subjects that are not able to wait or be observed for this period of time should not be considered for this study. Subjects will be randomized to intervention at the baseline visit of observation. Crossover between different treatment arms (RFA vs. AADs) is not encouraged and will not be allowed before 6-month follow-up duration of the treatment period, unless considered critical for the subject's well-being.

ii) Treatment or intervention arms will consist of: Antiarrhythmic drug (AAD) therapy. AAD therapy of choice is amiodarone due to its proven safety in subjects with LV dysfunction. Amiodarone loading dose of 10 grams is recommended, followed by maintenance dose of 200-400mg daily to achieve successful PVC suppression. We define successful PVC suppression only if  $\geq 80\%$  absolute reduction in PVC burden is achieved after a drug or intervention. Alternatively, sotalol and/or propafenone could be considered at the discretion of the electrophysiologist (sotalol dose of at least 120mg twice daily, propafenone 150-300mg tid) if there is a significant concern of safety profile of amiodarone. Finally, other AADs (class Ic) are acceptable if there is a clear preference by the clinical electrophysiologist while a rationale is requested for such choice. Overall, we suggest avoiding class Ia antiarrhythmic drugs due to the prior documented risk of pro-arrhythmia, however, they could be considered in subjects with an implantable or external defibrillator (Lifetest). Optimal heart failure medical therapy should be continued in combination with AAD throughout the 12-month follow-up. Throughout the 12-month follow up period, subjects will have a total of 5 visits to assess changes in clinical status, arrhythmia burden including PVCs and LVEF as outlined in Table 2 and Figure 1. In addition, subjects receiving amiodarone as antiarrhythmic (AAD group) will require a baseline TSH and LFTs and should be repeated every 6 months.

A 2-week ambulatory ECG Holter (Zio Patch, IRhythm, Inc.) will be obtained 4-6 weeks after initiation of AAD to assess whether PVC suppression was successful (defined above). If successful PVC suppression is not achieved, we will ask sites to consider either an increase in the antiarrhythmic dose or change of antiarrhythmic as noted above. A repeat 2-week ambulatory Holter monitor will be done 4 weeks after adjustment of AAD to re-assess PVC suppression.

Radiofrequency Ablation (RFA) of PVCs. RFA will be performed after completion of 3-month observation period). EPS will be performed on their baseline medications, except for antiarrhythmic drugs class II (beta blockers) which will be held at least 5 half-lives prior to procedure. Beta blockers should be resumed after RFA.

EPS and RFA will be performed using standard techniques and protocols similar to those subjects that do not participate in this clinical study. Multipolar electrode diagnostic catheters will be inserted. If no ectopy is present at baseline, isoproterenol may be infused at rates up to 10mcg/min. If the ectopy is infrequent despite adrenergic stimulation, pace mapping will be performed at a pacing cycle length determined by coupling interval of the spontaneous ventricular ectopy. RV or LV PVCs will be mapped/ablated at the discretion of the electrophysiologist. Coronary angiography and/or intracardiac echo will be performed as needed. RFA will be performed at the site of earliest endocardial activation or best pace map. RFA applications will be delivered for at least 30 seconds if adequate power at the electrode-tissue interface is achieved. RFA will be continued for at least 60-120 seconds in sites where PVCs are abolished within 30 seconds. After ablation of the PVCs, isoproterenol will be administered at 2-10 mcg/min as required to shorten sinus CL to 500ms to confirm that PVCs are not inducible by adrenergic stimulation. In the event of polymorphic PVCs, all morphologies are to be targeted for ablation. Subjects will be observed overnight in a telemetry bed and discharged home the next day, as it is current standard of care.

During enrollment and immediately after RFA, baseline medical therapy (including ACE inhibitors/ARB, beta blockers) should be optimized or continued throughout the 12-month follow-up period. Practitioners will be asked to document any changes in medical therapy including rationale. All events, side effects as well as change or decrease of doses will be documented and rationale explained. Similar to the AAD group, subjects will have 5 follow-up visits (Visit 2 – 6, Table 2 and Figure 1) to assess changes in clinical status, arrhythmia burden including PVCs and LVEF.

A 2-week ambulatory ECG Holter (Zio Patch, IRhythm, Inc.) will be obtained 4-6 weeks after RFA to assess whether PVC suppression was successful (defined above). If successful PVC suppression is not achieved, subjects will be offered a second PVC-RFA procedure 3 months after initial randomization. Redo-RFA will be performed with a similar approach as the first intervention; however, epicardial mapping will be encouraged if considered appropriate. This subgroup of subjects will have a repeat 2-week Holter monitor within 2-4 weeks after redo-RFA to document successful or failure of PVC suppression. All events and complications in the PVC suppression arm related to RFA will be documented.

